11.1. Sample Size Determination

According to the power analysis 40 per group should finish the study per group, in case of 20% drop outs, a minimum of 96 participants should be included.

12. DATA MANAGEMENT

The whole data collection procedure will be carried out through the ESMira App. ESMira is a tool for running longitudinal studies (ESM, AA, EMA, ...) with completely anonymized communication with participants and data collection. The following validated and frequently used mental health questionnaire will be used: Wellbeing (WHO-5), Depressive Symptoms (PHQ-9), Anxiety (GAD-7), Stress (PSS-10), Sleep quality (ISI), Eating disorder (EAT-8; SCOFF), and body awareness (BAD-2). These questionnaires will be collected at baseline, after intervention and at follow up. During the study, a weekly measurement of well being (WHO-5), body awareness (BAD-2), and stress (PSS-10) will be performed. What is ESMira? It works without a steady internet connection. All functionality of studies are saved locally in the app and saved data are cached and will be uploaded as soon as there is an internet connection. Personal Feedback: Researcher can set up complex charts that will be automatically calculated out of participants' data. These statistics can be either personalised to the participants or calculated out of all participants' data. Completely anonymous: Each participant gets a random participant id under which all data is collected. ESMira does not collect any personal data at any time. Anonymous Chat: Participants can communicate with the researcher from within the app and stay completely anonymous while doing so. Additionally, researchers can send important messages to all participants of a study. Free and open source: ESMira is developed as a project at Karl Landsteiner University to be used for our own studies and published for the community to use completely free of charge. Find out more at: https://github.com/KL-Psychological-Methodology/ESMira

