5. OBJECTIVES AND OUTCOME MEASURES

Objective, Research Question, Procedure, and Design

Clinical Trial Protocol Template version 14.0

CONFIDENTIAL

© Copyright: The University of Oxford and Oxford University Hospitals NHS Foundation Trust 2018

The aim of the planned study is to reduce the screen time of healthy students in Austria over a period of 3 weeks and to investigate its impact on mental health.

Mental health indicators were evaluated in both groups at baseline, post-intervention, and at follow-up (t2). Participants will be informed weekly via App.

1. Main outcomes

Well-being (WHO-5): The validated German version of the World Health Organization well-being questionnaire (WHO-5) will be used.

Depressive symptoms (PHQ-9):Depressive symptoms will be assessed using the Patient Health Questionnaire (PHQ-9) in the validated German version.

Stress (PSQ-20): Stress will be assessed using the German version of the 20-item short-form of the Perceived Stress Questionnaire.

Sleep quality (ISI): Sleep quality will be assessed with the Insomnia Severity Index (ISI).

2. Additional outcomes

Problematic smartphone use (Smartphone Addiction Scale (SAS-SV)), anxiety symptoms (GAD-7), disordered eating (SCOFF), and Body Appreciation (BAS-2) will further be assessed.

Physical activity will be measured using a fitness tracker, as well as heart rate variability (HRV) and resting heart rate.

Objectives	Outcome Measures	Timepoint(s) of evaluation of this outcome measure (if applicable)
Depressive Symptoms (PHQ-9) Well-Being (WHO-5) Stress (PSQ 20) Sleep quality (ISI)	 Patient Health Questionnaire (PHQ-9) World Health Organization well-being questionnaire (WHO-5) Perceived Stress Questionnaire (PSQ-20) Insomnia Severity Index (ISI) 	At Baseline, post- intervention and at Follow-up.
 Problematic Smartphone Use 	 Smartphone Addiction Scale SCOFF BAS-2 GAD-7 	At Baseline, post- intervention and at Follow-up.

Disordered Eating	
 Body Appreciation 	
 Anxiety 	

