8.7. Early Discontinuation/Withdrawal of Participants

Withdraw is possible at any time and without giving a reason. In case of withdrawal prior randomization, data won't be replaced. In case of withdrawel after randomization, missing data will be estimated by maximum likelihood estimation.

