10. SAFETY REPORTING

Participants will be informed that discomfort, burdensome, withdrawal symptoms, or unrest might be possible during 3-week intervention period. They will receive an emergency phone number for a psychological support if the symptoms were too stressful.

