11. STATISTIC ANALYSIS PLAN

We will use the statistic software IBM SPSS Statistics (IBM Corp., Armonk, NY, USA) to analyze the data. χ^2 -Test and independent samples tests will be used to examine differences at baseline (t0) regarding age, gender, smartphone screen time, physical activity per week, and mental health indicators between the control and the intervention group.

Clinical Trial Protocol Template version 14.0

CONFIDENTIAL

To examine the effect of reduced smartphone screen time on the mental health indicators, repeated measurements ANOVAs (rm-ANOVA) will be applied. The primary hypotheses focuses on the difference between t0 (baseline) and t1 (post-intervention) between control group and intervention group (between group effect). In a secondary analysis, the follow-up time point (t2) will also be included.

Group allocation (control vs. intervention) will be the between-group factor, time will be the within-group factor (t0, t1, t2). Furthermore, a sub-group analysis (rm-ANOVA) will be applied of those, who strictly adhered to the 2h smartphone screen time limit during all three weeks. In case of baseline group-differences in the mental health indicators, these variables will be added as a covariate in the rm-ANOVA. If the sphericity assumption will be violated, the Greenhouse-Geisser correction will be applied. In the post hoc tests, Bonferroni correction will be applied to adjust for multiple comparisons.

Missing values will be estimated with via maximum likelihood estimation.

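### WHO-5, a main outcome, is to be collected weekly, but the SAP gives the weekly scores no stated role, so the WHO-5 analysis forgoes a cheap protection against drop-out that differs between arms

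*Combined protocol and SAP*

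**What the plan says.** WHO-5 is listed among the main outcomes in the Synopsis (Section 3), Section 5 and Section 8.6. Section 5 schedules it at baseline, post-intervention and follow-up. Section 12 repeats those three occasions and adds: "During the study, a weekly measurement of well being (WHO-5), body awareness (BAD-2), and stress (PSS-10) will be performed". It does not limit this to one arm.

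Section 11 prescribes repeated-measures ANOVA: "Group allocation (control vs. intervention) will be the between-group factor, time will be the within-group factor (t0, t1, t2"), t2 being follow-up. For the main comparison, "The primary hypotheses focuses on the difference between t0 (baseline) and t1 (post-intervention) between control group and intervention group". No analysis in Section 11 mentions a weekly score.

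On missing data, Section 11 says "Missing values will be estimated with via maximum likelihood estimation" and Section 8.7 says "In case of withdrawel after randomization, missing data will be estimated by maximum likelihood estimation". Neither names the variables in the likelihood.

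Section 10 says participants will be told that "discomfort, burdensome, withdrawal symptoms, or unrest might be possible during 3-week intervention period". The time labels below are those of Section 11; the Lay Summary and Section 9 number the occasions differently.

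**The concern.** Maximum likelihood protects against selective drop-out only to the extent that the data explaining the drop-out are in the model. In a model containing t0 and t1 only, a person who leaves after week 1 or 2 is represented by t0. Their WHO-5 scores under the screen-time limit would already be in the app's database, and these are the values most likely to say why they left and where they were heading.

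The two arms face different pressures during those weeks. The intervention arm is restricted and warned of possible discomfort. Controls carry on unchanged and, under Sections 6 and 9, are offered the intervention after follow-up to limit drop-out. A difference in who leaves is therefore plausible. If it occurs, the WHO-5 effect is distorted even though the data to correct much of it may be in hand. Deciding on the weekly scores after the data are seen would be a data-dependent choice in an unblinded trial.

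**Working it through.** **The plan's own figures.** The Synopsis gives d = 0.45, power .8, significance level .05, icc = .05, 40 completers per group and 20% drop-out. Treating the comparison as a between-group effect on the mean of two measurements, the variance factor is (1 + 0.05)/2 = 0.525, and n = 2 × (1.96 + 0.842)² × 0.525 / 0.45² = 40.7, or 41 per group. This is close to the stated 40. The point made here does not alter N. Of the 96 (Section 11.1) to 100 (Synopsis) recruited, 20% is about 19 to 20 people.

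**What must be assumed.** The documents give no correlations between occasions and no drop-out mechanism. The runs below assume two weekly scores before t1, and that people with lower recent WHO-5 are likelier to leave.

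**Simulation 1.** 400,000 per arm, true effect 0.45 SD. The correlation of t0 with later scores is .4 or .6, and that among weekly scores and t1 is .7 or .8. Drop-out depends on the week-2 score, with log-odds of 1 (or 0.5) per SD. Bias is the estimate minus the full-data estimate. For example, with correlations .4 and .7 and 20% drop-out in each arm, score-driven in the intervention arm only, it is 0.546 − 0.450 = +0.096.

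| Drop-out, control/intervention | Score-driven in | Bias, ML on t0 and t1 | Bias, change score in completers | Bias, ML with weekly scores |
|---|---|---|---|---|
| 20/20% | both arms alike | 0.00 | 0.00 | 0.00 |
| 20/20%, slope 0.5 | intervention only | +0.03 to +0.06 | +0.01 to +0.04 | 0.00 |
| 20/20%, slope 1 | intervention only | +0.06 to +0.11 | +0.02 to +0.07 | 0.00 |
| 10/30%, slope 1 | both arms, same slope | +0.06 to +0.11 | +0.02 to +0.07 | 0.00 |
| 10/30%, slope 1 | intervention only | +0.09 to +0.17 | +0.03 to +0.11 | 0.00 |

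The last column is within 0.002 in every cell. It is zero by construction, because simulated drop-out depends only on a recorded score. The completers' change score is what the group-by-time term reduces to with two occasions. It is less biased here, but not unbiased.

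**Simulation 2.** No true effect; drop-out after week 1 and week 2 by the last weekly score, in the intervention arm only. The t0 correlations are .5 to .7, adjacent-week correlations .7 to .8, and slopes 0.7 to 1.0. The t0/t1 bias is +0.04 to +0.10 SD at about 20% drop-out per arm and +0.02 to +0.05 SD at 10%. With the same mechanism and rate in both arms it is nil. Exchanging the arms changes the sign.

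**Scale.** Against d = 0.45, the bias is 0.02/0.45 = 4% to 0.10/0.45 = 22% of the planned effect. The standard error of the t0-adjusted difference at 40 per group is √[2(1 − ρ²)/40], which is 0.194 at ρ = .5 and 0.160 at ρ = .7. A bias of 0.10 SD at ρ = .5 is 0.10/0.194 = 0.52 standard errors. The two-sided 5% error rate then becomes P(Z > 1.44) + P(Z < −2.48) = 0.075 + 0.007, or about 8%. A bias of 0.02 SD leaves it at about 5%. In a run with 50 per group, adding the weekly scores also lowered the variance of the t1 contrast by 3 to 5%, including under random drop-out.

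**The case against.** A reader might infer more than the documents support, in five ways.

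- *The planned analysis favours the intervention.* That needs a between-arm difference in mechanism or rate, which the documents do not state. Section 10 says symptoms are possible and does not link them to leaving; Section 13.3 offers the tracker as a reason to complete. Section 6 shows concern about control drop-out, and if unhappy controls leave more, the bias runs the other way.
- *Weekly scores are discarded whatever likelihood method is used.* The maximum-likelihood sentences name no variables. Estimation with weekly WHO-5 as auxiliary data would fit the text, so the gap is one of specification.
- *Adding weekly scores removes the bias.* Only where leaving depends on recorded scores.
- *All of the 20% is lost in the intervention weeks.* Section 11.1 concerns finishing the study. Some losses will come after t1, where the primary contrast is untouched, or before any weekly score, where the remedy cannot help.
- *The same remedy serves other outcomes, or a second baseline.* Weekly stress is PSS-10 whereas the main stress outcome is PSQ-20; PHQ-9 and ISI are not listed as weekly; the body scale is not a main outcome. Section 9 places randomisation before the 10-day phase, so a weekly value from that phase is not a pre-randomisation covariate.

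It is also fair to object that the weekly WHO-5 schedule is insecure. It appears only in Section 12, whose instrument list differs from that of Section 5.

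All of this limits the size and reach of the point. It does not supply the missing statement of what the weekly WHO-5 scores are for.

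**Conclusion.** The point holds as a modest, inexpensive improvement for one of the four main outcomes. The SAP plans weekly WHO-5 and assigns it no role. Bias of roughly +0.02 to +0.10 SD in the t0/t1 analysis is conditional on score-driven drop-out in the intervention arm only, equal drop-out of 10 to 20% per arm, and correlations of .5 to .8. Weaker correlation with t0, or unequal drop-out rates, gives more; identical drop-out in both arms gives none. Neither the size nor the direction can be read from the documents. The plan is not shown to be biased. It leaves unused the information that would guard against one plausible form of bias.

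**What to change.** In Section 11, for WHO-5 only, state one of the following:

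- a likelihood-based repeated-measures model fitted to t0, the weekly intervention-period scores and t1, with group-by-week means and unstructured covariance (a weekly score that coincides with t1 is counted once); or
- the weekly scores entered as auxiliary variables in the maximum-likelihood estimation already promised.

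In either case, keep the t1 group difference adjusted for t0 as the primary contrast. First reconcile Sections 5 and 12, and confirm that weekly WHO-5 is collected in both arms, since the model needs weekly control data.

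The cost is SAP wording and slightly more analysis work. If Section 12 stands, no data collection is added and N does not change. Four occasions (t0, two weekly scores, t1) need 4 × 5/2 = 10 covariance parameters, which is manageable with 96 to 100 participants. The remaining weakness is drop-out driven by unrecorded scores or occurring before any weekly score. This change does not correct it, and the SAP should say so.

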13. ETHICAL AND REGULATORY CONSIDERATIONS

13.1. Declaration of Helsinki

The Investigator will ensure that this trial is conducted in accordance with the principles of the Declaration of Helsinki.

13.2. Guidelines for Good Clinical Practice

The Investigator will ensure that this trial is conducted in accordance with relevant regulations and with Good Clinical Practice.

13.3. Incentives

Participants can keep the fitness tracker after completing the study as an incentive.

14. FINANCE AND INSURANCE

14.1. Funding

No funding, however, the fitness tracker will be sponsored by University.
